#### **9.2.5. Follow-Up Period**

##### **9.2.5.1. SCRI**

In the SCRI analysis, follow-up for the risk period will begin upon (for the outcomes of anaphylaxis and convulsions/seizures) or one day after (for all other outcomes) receipt of the COMIRNATY 2023-2024 Formula ([Table 2](#)) and continue until the earliest of:

- Receipt of a COVID-19 vaccine other than the COMIRNATY 2023-2024 Formula;
- The end of the outcome-specific risk interval as defined in [Section 9.3.2](#);
- Disenrollment from the health plan, death, or the end of data collection.

After the outcome-specific pre-specified washout period following the risk interval, follow-up for the control period will begin and continue until the earliest of:

- Receipt of a COVID-19 vaccine other than the COMIRNATY 2023-2024 Formula;
- The end of the control period as defined in [Section 9.3.2](#);
- Disenrollment from the health plan, death, or the end of data collection.

Individuals will be followed for each safety outcome during both the risk and control periods, such that events observed during the risk period or washout period will not censor follow-up for the control period.

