### 9.3.1.2. Comparator Cohort

The Phase 2 cohort study will include comparators with no recorded vaccination for the COMIRNATY 2023-2024 Formula. To improve comparability with the COMIRNATY 2023-2024 Formula vaccinated cohort, patients included in the comparator cohort will be required to have a code indicative of a healthcare encounter, including one of the following:

- Presence of a code for a vaccine other than the COMIRNATY 2023-2024 Formula;
- Presence of a code indicative of an outpatient healthcare encounter.

Codes relating to other vaccines or outpatient visits are provided in [Annex 2 \(Appendix II\)](#).

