### 9.3.2. Outcomes

In both the SCRI and cohort studies, the pre-specified safety outcomes of interest will include the following:

- ADEM
- Anaphylaxis
- Bell's palsy
- CVST
- Convulsions/seizures (non-febrile)
- Encephalomyelitis
- Glomerulonephritis
- Guillain-Barré syndrome
- Herpes zoster
- Immune-mediated myositis
- Immune thrombocytopenia
- Kawasaki disease
- Multi inflammatory syndrome (in children and adults)
- MS
- MI
- Myocarditis/pericarditis
- PE
- Stroke, hemorrhagic
- Stroke, ischemic
- Transverse myelitis

In addition, in Phase 2 of the study, the following pregnancy outcomes will be assessed in pregnant women or their infants, if sample size permits:

- Spontaneous abortion
- Stillbirth
- Preterm birth
- Major congenital malformations
- Small for gestational age

Code lists for the safety outcomes of interest are provided in [Annex 2 \(Appendix III\)](#). Corresponding site of care requirements are listed in Table 2. When possible, outcomes will be defined using a validated claims-based algorithm with high performance ([CBER, 2021](#)).

If a safety signal is detected in the interim report, then medical records will be retrieved for a subset of participants to confirm the presence of that study outcome. A safety signal that requires confirmation through medical record review will be defined as a rate ratio of > 3.0 and a corresponding P value of < 0.01 in the primary analysis of the SCRI design (details in [Section 9.7.1.1](#)). Additionally, medical record review may be conducted for analyses beyond the primary SCRI analysis if a safety signal (defined as a rate ratio of > 3.0 and a corresponding P value of < 0.01) is detected in the interim or final report. Medical records may also be retrieved for AESIs with estimates approaching the pre-specified safety signal threshold.

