### 9.3.2.1. Outcome-Specific Risk and Control Periods

The SCRI design ([Section 9.1.1](#)) requires that clean periods, risk intervals, washout periods, and control intervals be specified for every study outcome. The lengths of the clean periods and risk intervals are listed in [Table 2](#). The washout period for all outcomes will begin immediately after the end of the risk interval and continue for 30 days ([Akpandak et al., 2022](#)); the control period will follow the washout period and be equivalent in length to the risk interval. Interval lengths were determined based on prior vaccine literature, including COVID-19 vaccine studies conducted as part of the FDA’s Center for Biologics Evaluation and Research (CBER) Biologics Effectiveness and Safety (BEST) System ([Akpandak et al., 2022](#); [Barda et al., 2021](#); [CBER, 2021](#); [Joy et al., 2023](#); [Klein et al., 2021](#); [Liu et al., 2023](#); [Martin et al., 2021](#); [McCarthy et al., 2013](#); [Wack et al., 2021](#)).

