### 17.3. Appendix III – Safety Outcomes of Interest

All codes are ICD-10 diagnosis codes; all outcomes will be defined based on the presence of a single code unless otherwise specified. In order to qualify as an outcome, the outcome-specific codes must be identified during emergency department visits, inpatient hospitalizations, or outpatient visits, as detailed in [Table 2](#). Outpatient visits are defined through physician evaluation and management codes ([Section 17.2.3](#)).

\* Outcome codes marked with an asterisk are based on COVID-19 vaccine studies conducted as part of the FDA’s CBER BEST system.

- Acute disseminated encephalomyelitis (ADEM)\*
  - G04.00 – Acute disseminated encephalitis and encephalomyelitis, unspecified
- Anaphylaxis\*
  - T80.52XA – Anaphylactic reaction due to vaccination, initial encounter
  - T78.2XXA – Anaphylactic shock, unspecified, initial encounter
- Bell's palsy\*
  - G51.0 – Bell’s palsy
  - G51.8 – Other disorders of facial nerve
  - G51.9 – Disorder of facial nerve, unspecified
- Cerebral venous sinus thrombosis (CVST)
  - I67.6 – Nonpyogenic thrombosis of intracranial venous system
  - I63.6 – Cerebral infarction due to cerebral venous thrombosis, nonpyogenic
- Convulsions/seizures (non-febrile)
  - G40.001 – Localization-related (focal) (partial) idiopathic epilepsy and epileptic syndromes with seizures of localized onset, not intractable, with status epilepticus
  - G40.009 – Localization-related (focal) (partial) idiopathic epilepsy and epileptic syndromes with seizures of localized onset, not intractable, without status epilepticus
  - G40.011 – Localization-related (focal) (partial) idiopathic epilepsy and epileptic syndromes with seizures of localized onset, intractable, with status epilepticus
  - G40.019 – Localization-related (focal) (partial) idiopathic epilepsy and epileptic syndromes with seizures of localized onset, intractable, without status epilepticus
  - G40.101 – Localization-related (focal) (partial) symptomatic epilepsy and epileptic syndromes with simple partial seizures, not intractable, with status epilepticus

090177e1a5be86fe\Approved\Approved On: 19-Mar-2026 15:57 (GMT)

- G40.109 – Localization-related (focal) (partial) symptomatic epilepsy and epileptic syndromes with simple partial seizures, not intractable, without status epilepticus

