- G40.812 – Lennox-Gastaut syndrome, not intractable, without status epilepticus
- G40.813 – Lennox-Gastaut syndrome, intractable, with status epilepticus
- G40.814 – Lennox-Gastaut syndrome, intractable, without status epilepticus
- G40.821 – Epileptic spasms, not intractable, with status epilepticus
- G40.822 – Epileptic spasms, not intractable, without status epilepticus
- G40.823 – Epileptic spasms, intractable, with status epilepticus
- G40.824 – Epileptic spasms, intractable, without status epilepticus
- G40.89 – Other seizures
- G40.901 – Epilepsy, unspecified, not intractable, with status epilepticus
- G40.909 – Epilepsy, unspecified, not intractable, without status epilepticus
- G40.911 – Epilepsy, unspecified, intractable, with status epilepticus
- G40.919 – Epilepsy, unspecified, intractable, without status epilepticus
- G40.A01 – Absence epileptic syndrome, not intractable, with status epilepticus
- G40.A09 – Absence epileptic syndrome, not intractable, without status epilepticus
- G40.A11 – Absence epileptic syndrome, intractable, with status epilepticus
- G40.A19 – Absence epileptic syndrome, intractable, without status epilepticus
- G40.B01 – Juvenile myoclonic epilepsy, not intractable, with status epilepticus
- G40.B09 – Juvenile myoclonic epilepsy, not intractable, without status epilepticus
- G40.B11 – Juvenile myoclonic epilepsy, intractable, with status epilepticus
- G40.B19 – Juvenile myoclonic epilepsy, intractable, without status epilepticus
- R56.1 – Post traumatic seizures
- R56.9 – Unspecified convulsions

- Encephalomyelitis\*
  - G04.02 – Postimmunization acute disseminated encephalitis, myelitis, and encephalomyelitis
  - G04.00 – Acute disseminated encephalitis and encephalomyelitis, unspecified
  - G04.81 – Other encephalitis and encephalomyelitis
  - G04.90 – Encephalitis and encephalomyelitis
  - G05.3 – Encephalitis and encephalomyelitis in diseases classified elsewhere
- Glomerulonephritis
  - N06.A Isolated proteinuria with C3 glomerulonephritis
  - N06.7 Isolated proteinuria with diffuse crescentic glomerulonephritis
  - N06.5 Isolated proteinuria with diffuse mesangiocapillary glomerulonephritis
  - N06.4 Isolated proteinuria with diffuse endocapillary proliferative glomerulonephritis
  - N04.A Nephrotic syndrome with C3 glomerulonephritis
  - N04.2 Nephrotic syndrome with diffuse membranous glomerulonephritis
  - N04.7 Nephrotic syndrome with diffuse crescentic glomerulonephritis

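### ADEM is defined by G04.00 alone, so a case coded only as post-immunization ADEM (G04.02) is not an ADEM event; if that code clusters soon after vaccination, the SCRI rate ratio for ADEM is biased downward

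*Protocol*

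**What the plan says.** The protocol calls itself a combined protocol and SAP (Section 7), and Annex 1 lists no standalone documents, so the code lists in Appendix III are the working outcome definitions.

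- **ADEM** has a single entry in Section 17.3: "G04.00 – Acute disseminated encephalitis and encephalomyelitis, unspecified".
- **Encephalomyelitis** is a separate outcome. It lists G04.00 again, together with "G04.02 – Postimmunization acute disseminated encephalitis, myelitis, and encephalomyelitis", G04.81, G04.90 and G05.3.
- **Counting rule** (17.3): "all outcomes will be defined based on the presence of a single code unless otherwise specified". Nothing further is specified for ADEM.
- **Source** (17.3): "Outcome codes marked with an asterisk are based on COVID-19 vaccine studies conducted as part of the" FDA's CBER BEST system. Both outcomes carry the asterisk.
- **Windows** (Table 2, both outcomes inpatient only): ADEM has a clean period of Days -28 to -1 and a risk interval of Days 0 to 21. Encephalomyelitis has a clean period of Days -183 to 0 and a risk interval of Days 1 to 42.
- **Control period** (9.3.2.1): after a 30-day washout, "the control period will follow the washout period and be equivalent in length to the risk interval".
- **Start of follow-up** (9.2.5.1): "follow-up for the risk period will begin upon (for the outcomes of anaphylaxis and convulsions/seizures) or one day after (for all other outcomes"), which leaves ADEM in the second group.

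**The concern.** G04.02 is, by its own label, a code for disease after immunization. A hospital is more likely to use it three weeks after a vaccine than two months after, and more likely in a vaccinee than in someone with no recent vaccine. If so, whether a true ADEM case is captured depends on exposure and on time since vaccination, and the missed cases fall mainly in the risk window. Misclassification of that kind works against finding the risk the outcome was chosen to detect.

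The appendix also treats a similar outcome differently. Anaphylaxis pairs the vaccine-attributed code (T80.52XA) with the unspecified one (T78.2XXA). For ADEM only the unspecified code is kept, and no reason is given.

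The practical stake is the signal rule in Section 9.3.2. Medical record confirmation is required in the interim report when the primary SCRI analysis shows "a rate ratio of > 3.0 and a corresponding P value of < 0.01". An attenuated ratio may miss it.

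**Working it through.** The protocol gives no event count, power or expected rate for ADEM, so there is no figure of its own to reproduce.

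**1. Windows.** With a Day 0 start, the risk interval is Days 0 to 21 (22 days), the washout Days 22 to 51 (30 days) and the control period Days 52 to 73 (22 days). The windows are equal, so the rate ratio is the ratio of counts, apart from censoring.

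**2. Bias factor.** Let f and g be the shares of true ADEM cases coded only G04.02 in the risk and control windows. The retained counts are (1 − f) and (1 − g) times the true counts, so

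observed RR = true RR × (1 − f)/(1 − g).

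There is no bias if f = g, and the bias is downward if f > g.

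**3. Size under assumed shares.** Neither f nor g is in the protocol.

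| True RR | f = 10%, g = 0 | f = 25%, g = 0 | f = 25%, g = 5% | f = 50%, g = 0 |
|---|---|---|---|---|
| 1 | 0.90 | 0.75 | 0.79 | 0.50 |
| 2 | 1.80 | 1.50 | 1.58 | 1.00 |
| 4 | 3.60 | 3.00 | 3.16 | 2.00 |

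With g = 0, the share that pulls the ratio down to 3.0 is f = 1 − 3/RR: 14% for a true ratio of 3.5, 25% for 4 and 40% for 5.

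**4. Signal rule, assumed counts.** This uses the exact two-sided binomial test with probability 0.5.

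- All cases captured, 20 against 5: RR = 4.0, P = 0.0041, a signal.
- Five of the 20 coded only G04.02, so 15 against 5: RR = 3.0, P = 0.041, no signal.

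**5. Cohort phase.** Follow-up runs up to one year, and late events are unlikely to be coded as post-immunization. Assume a constant baseline of one unit per day over 365 days, a fourfold rate in the first 22 days only, and no G04.02 coding in comparators.

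- True total: 22 × 4 + 343 = 431. Ratio: 431/365 = 1.18.
- With half of the early cases lost: 44 + 343 = 387. Ratio: 387/365 = 1.06.

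The factor is 387/431 = 0.90, against 0.50 in the SCRI at the same early share. It is closer to 1 again where comparators entered on another vaccine and can themselves be coded G04.02.

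**6. Day 0.** Table 2 gives ADEM a 22-day risk interval with control Days 52 to 73. Under Section 9.2.5.1 it would be Days 1 to 21 (21 days) with control Days 52 to 72. Day 0 would then lie in neither the clean period, which ends on Day -1, nor the risk interval.

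**The case against.** **The cases are not lost to the study.** This stands. A reader might infer that vaccine-attributed ADEM disappears, but G04.02 counts under Encephalomyelitis, which is pre-specified in both designs, is also inpatient, and covers Days 1 to 21 within its Days 1 to 42. Only cases coded solely G04.02 leave the ADEM outcome, since any inpatient G04.00 code qualifies. What remains is that ADEM is its own outcome. Under Encephalomyelitis these cases are mixed with broader codes over a longer window that omits Day 0. How far that dilutes an early excess cannot be computed from the protocol.

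**The list has a regulatory source.** Keeping a list derived from BEST studies is defensible, and that source cannot be checked here. But a source does not make capture independent of exposure, and the protocol says only that the codes are based on those studies.

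**Adding G04.02 can bias upward.** This is the strongest point. G04.02 is an attribution code, and its label also covers myelitis. A clinician may apply it to a non-ADEM illness because of a recent vaccine. Illustration with assumed counts: 10 against 10 true cases plus 5 such cases in the risk window gives 15/10 = 1.5 with no true effect. This does not justify leaving the code out without comment, but it means that neither definition alone is enough.

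**The threshold consequence is limited.** Section 9.3.2 also allows record retrieval for estimates approaching the threshold, and estimates with intervals are reported regardless. A reader might also infer that the omission is what stops a true ratio of 3 from signalling. It is not: with f = 0 such a ratio reads exactly 3.0, which does not exceed 3.0 either.

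**The SCRI formula does not carry over to the cohort.** Agreed. Follow-up is up to a year, and a qualifying comparator encounter includes "Presence of a code for a vaccine other than the COMIRNATY 2023-2024 Formula".

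**Conclusion.** The concern holds conditionally. It is plain from the text that a case coded only G04.02 is not an ADEM event, and that no reason is given. The downward bias in the SCRI ADEM ratio rests on one assumption, that f exceeds g. The code's label makes this likely, but the protocol does not establish it. At assumed f of 10% to 50% with g = 0, the loss is 10% to 50% of the ratio: a true 4 reads 3.6 to 2.0. In the cohort the effect is likely smaller. To say outright that the ADEM rate ratio is biased downward in both phases would go beyond what the protocol supports.

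The Day 0 conflict is a separate, minor inconsistency. It is certain on the text, affects one day of a 22-day window, and lends no support to the coding point.

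**What to change.** 1. In Section 17.3, define ADEM as G04.00 or G04.02.
2. Report ADEM on G04.00 alone as a paired sensitivity analysis in both phases. The pair brackets under-capture without G04.02 and possible over-capture, through diagnostic suspicion or myelitis, with it. The G04.00 row also keeps comparability with the asterisked source list.
3. Tabulate ADEM events by code and by window, so that the share coded only G04.02 is seen rather than assumed.
4. Reconcile Table 2 and Section 9.2.5.1 on the ADEM start day. The choice sets the length of the risk interval and, through Section 9.3.2.1, that of the control period.

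The cost is one code already in the study's outcome lists, one extra row per ADEM analysis, one short table and one corrected sentence or table cell. The real downside is the possible over-capture, which is why the paired row is part of the change and not optional.

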#### 9.1.1. SCRI

Phase 1 will monitor the incidence rate of pre-specified safety events of interest in a general population of individuals who receive the COMIRNATY 2023-2024 Formula using an SCRI study design that tracks post-vaccination risk intervals and control (reference) periods for each vaccinated individual. Monitoring will be conducted during a pre-specified risk period immediately following vaccination, and the observed rate of events during this risk period will be compared to that of a control period temporally removed from the vaccination event. As depicted in [Figure 1](#), only individuals who receive the COMIRNATY 2023-2024 Formula will be included in the SCRI study ([Baker et al., 2015](#)). Within each individual, outcomes occurring during the risk interval will be compared with those occurring during the control period, in order to determine whether these outcomes occur more frequently immediately after vaccination as compared with a reference period. A washout period may be inserted between the risk interval and the control period to ensure that events relating to the vaccine are not incorrectly attributed to the control period. To ensure that observed outcomes are truly incident, a period free from the outcome of interest (clean period) may be required prior to vaccination.

090177e1a5be86fe\Approved\Approved On: 19-Mar-2026 15:57 (GMT)

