#### **9.2.4. Baseline Period**

The baseline period will consist of all continuously enrolled available time up to one year (365 days) prior to the vaccination date (SCRI) or cohort entry date (cohort study). Recognizing that narrower or specific windows of assessment may better capture select patient attributes of interest, specific covariates may be assessed using alternate time period(s). In this study, all individuals are required to have a minimum of 365 days of continuous health plan enrollment prior to the vaccination or cohort entry date (Sections 9.2.1.1 and 9.2.2.1), or continuous enrollment since birth if the vaccination or cohort entry date occurred at  $< 1$  year of age.

In both study designs, some or all of the baseline period will be used to exclude individuals with prevalent outcomes prior to vaccination or cohort entry date. This portion of the baseline period will be referred to as the ‘clean period.’ For a list of outcome-specific clean periods, please see [Section 9.3.2](#).

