**Table 2. Clean periods and risk intervals for safety outcomes of interest**

Outcome	Clean Period*	Vaccine Risk Interval*	Care Setting**
Acute disseminated encephalomyelitis	Days -28 to -1	Days 0 to 21	IP
Anaphylaxis	Days -30 to -1	Days 0 to 1	IP, ED
Bell's palsy	Days -183 to 0	Days 1 to 42	IP, OP
Cerebral venous sinus thrombosis	Days -365 to 0	Days 1 to 28	IP, OP
Convulsions/seizures, non-febrile	Days -42 to -1	Days 0 to 21	IP, OP
Encephalomyelitis	Days -183 to 0	Days 1 to 42	IP
Glomerulonephritis	Days -365 to 0***	Days 1 to 42***	IP, OP
Guillain-Barré syndrome	Days -365 to 0	Days 1 to 42	IP-primary position only
Herpes zoster	Days -270 to 0	Days 1 to 30	IP, OP
Immune-mediated myositis	Days -365 to 0***	Days 1 to 28	IP, OP
Immune thrombocytopenia	Days -365 to 0	Days 1 to 42	IP, OP
Kawasaki disease	Days -365 to 0	Days 1 to 21	IP, OP
Multi inflammatory syndrome	Days -365 to 0	Days 1 to 42	IP, ED
Multiple sclerosis	Days -365 to 0	Days 1 to 42***	IP, OP
Myocardial infarction	Days -365 to 0	Days 1 to 28	IP
Myocarditis/pericarditis	Days -365 to 0	Days 1 to 21	IP, OP

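### The non-febrile seizure outcome accepts any single outpatient epilepsy code after only 42 clean days, so routine visits of people with known epilepsy can be counted as incident seizures in both phases

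*Protocol*

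**What the plan says.** Section 17.3 sets the general rule that "all outcomes will be defined based on the presence of a single code unless otherwise specified". The non-febrile seizure list adds no further condition. It is almost wholly G40.x, including disease-state entries such as G40.909 ("Epilepsy, unspecified, not intractable, without status epilepticus"), juvenile myoclonic epilepsy and Lennox-Gastaut syndrome without status epilepticus, plus G40.89, R56.1 and R56.9. No primary-position, first-diagnosis or prior-epilepsy rule is attached.

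In Table 2 the row "Convulsions/seizures, non-febrile" has a clean period of Days -42 to -1, a risk interval of Days 0 to 21, and inpatient and outpatient settings. On the outpatient side, "Outpatient visits are defined through physician evaluation and management codes"; the codes in Section 17.2.3 include preventive visits.

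Section 9.1.1 gives the purpose of the clean period: "To ensure that observed outcomes are truly incident, a period free from the outcome of interest (clean period) may be required prior to vaccination". Section 9.2.4 states that "all individuals are required to have a minimum of 365 days of continuous health plan enrollment prior to the vaccination or cohort entry date", with enrolment since birth accepted for infants under one year. The data for a longer look-back are therefore already required.

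**The concern.** A G40 code at an office visit usually records that the person has epilepsy, not that a seizure has just happened. Someone seen every three months has a good chance of no coded visit in the previous 42 days. That person enters as outcome-free, and the next routine visit is an event.

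Table 2 gives 17 of the 20 outcomes a clean period of 183 to 365 days. The three shorter ones are ADEM (28 days, inpatient only), anaphylaxis (30 days, inpatient and emergency department) and seizures. Seizure is the only one of these three that admits outpatient codes.

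Two things are at stake. In Phase 2, prevalent epilepsy can swamp the event count and hide an effect on new-onset seizures. Follow-up also ends at the first outcome (Section 9.2.5.2), so a routine visit removes the person before any later real seizure. The neurological covariate list (Section 17.4.1.10) runs from F70 to F89 without G40, so prevalent epilepsy is neither excluded nor pre-specified in the propensity score. In the self-controlled analysis, a visit-free period is required before the risk window but not before the control window, which can tilt the ratio.

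**Working it through.** The protocol gives no event count or power figure for this outcome, so there is no stated figure to reproduce.

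**Phase 2 dilution**

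Assumed inputs, none of them in the protocol:
- epilepsy prevalence 0.5-1%;
- 70-90% of these people have a coded visit within the year;
- 50-100 new-onset seizures per 100,000 per year.

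The share passing the clean period is 1 - 42/T for regular visits every T days: 1 - 42/90 = 0.53 and 1 - 42/180 = 0.77.

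Prevalent events per 100,000 = prevalence × share seen × share passing. A true ratio of 2 confined to new-onset seizures reads as (2 × incident + prevalent) / (incident + prevalent).

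- Mildest corner: 500 × 0.70 × 0.53 = 185.5 prevalent against 100 incident. Prevalent share 185.5/285.5 = 65%. The ratio reads 385.5/285.5 = 1.35.
- Severest corner: 1,000 × 0.90 × 0.77 = 693 prevalent against 50 incident. Prevalent share 693/743 = 93%. The ratio reads 793/743 = 1.07.

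**Self-controlled analysis**

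Table 2 gives the risk window as Days 0-21. The washout starts "immediately after the end of the risk interval and continue for 30 days" (Days 22-51), and the control window has the same length as the risk window (Days 52-73). Section 9.7.1.1 keeps people with an event in one window only. I simulated people with known epilepsy, routine coded visits, no new seizures and no vaccine effect. I applied the 42-day rule and took risk-only over control-only cases. Visit spacing is assumed, and CV is the coefficient of variation of the gap between visits.

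| Mean gap | CV 0.15 | CV 0.3 | CV 0.5 | Random |
|---|---|---|---|---|
| 60 days | about 35 | 5.7-6.0 | 2.1 | 1.0 |
| 90 days | 6.1-6.2 | 2.7-2.8 | 1.6 | 1.0 |
| 120 days | 1.3 | 1.5 | 1.4 | 1.0 |
| 180 days | 1.0 | 1.1 | 1.2 | 1.0 |
| 365 days | 1.0 | 1.0 | 1.0 | 1.0 |

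Without the clean-period filter every cell returns about 1.0, so the filter creates the excess. No visit in the last 42 days means a regular visitor is due soon after Day 0.

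Real patients have mixed intervals. With assumed shares of 10/20/20/30/20% at 60/90/120/180/365 days, the ratio is 1.68, 1.56 and 1.36 at CV 0.15, 0.3 and 0.5. With equal fifths it is 1.92, 1.76 and 1.44. Random visits give 1.0 in both mixes.

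**The same simulation with a 365-day look-back**

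- Regular visitors at 60-180 days: at most 1.4% remain eligible, against 30-77% under 42 days.
- False window events across the mixes: down about 88-97%.
- Regular near-annual visitors: about 6-20% still qualify. Within that group the ratio is about 3.2, 1.6 and 1.3 at CV 0.15, 0.3 and 0.5, where the 42-day rule gave 1.0.

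**The case against.** A reader might infer that this definition will generate a false safety signal in the self-controlled analysis, that is, a ratio above 3.0 with P below 0.01 as set in Section 9.3.2. The protocol does not support that. It gives no visit spacing. A ratio above 3.0 arises only where nearly everyone has regular visits about two to three months apart. The assumed mixtures stay below 2, and genuine acute seizures would dilute the excess further.

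Nor does the endpoint measure scheduling alone. Inpatient events, R56.1, R56.9, G40.89 and the status epilepticus codes all count.

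The Phase 2 dilution uses external assumptions and takes the vaccine effect to be zero in people with known epilepsy. Breakthrough seizures there are a plausible safety event. Its severest corner uses 180-day visits, where the self-controlled bias is close to nil, so the two harms do not peak together.

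A short clean period also suits an episodic outcome. Section 9.3.2.1 says the intervals come from prior literature, and the seizure row is not among those marked in Table 2 as undeterminable from it.

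These points limit the size of the problem, not its existence. The literature basis cannot be checked here, and the seizure code list lacks the asterisk that marks lists based on the FDA programme's studies. Record review is mandatory only for an interim signal in the primary self-controlled analysis. It does not correct the estimate, and an effect masked toward 1 would not trigger it. The caveat in Section 9.9 about miscoded diagnoses does not cover epilepsy that is correctly coded but prevalent.

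**Conclusion.** The concern stands as a problem of outcome specificity for one of the 20 safety outcomes, and it should be fixed. The definition lets routine visits of people with known epilepsy count as incident seizures in both phases, and no other stated rule removes them.

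The main consequence is in Phase 2 and does not need regular visits: about 65-93% of events prevalent, and a true ratio of 2 in new-onset seizures reading about 1.07-1.35, under the assumptions listed. In the self-controlled analysis the effect is conditional: none for random visits, about 1.0-1.2 at 180 days, and about 1.3-1.7 in the mixture weighted to longer intervals (up to 1.9 with equal fifths). It passes 3.0 only if most patients have regular two-to-three-month visits. Where visits fall evenly across both windows, the extra events pull the ratio toward 1.

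The mechanism is certain from the text. Confidence in its size is moderate, because prevalence, incidence and visit spacing are all assumed.

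**What to change.** In Table 2 and Section 17.3, count an outpatient seizure code as an event only if no G40.x, R56.1 or R56.9 code appears in any setting in Days -365 to -1. Keep Days -42 to -1 for inpatient events, so that acute seizures in known epilepsy are still captured. The emergency department is not a listed setting for this outcome, so the rule should not refer to it unless Table 2 is changed. Report the present definition as a sensitivity analysis.

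The cost is a setting-specific clean period in one Table 2 row and matching text in Section 17.3. No new data are needed, because the 365-day enrolment is already required.

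Two downsides should be stated. Breakthrough seizures in known epilepsy that are seen only in an office are no longer counted. A small group of near-annual visitors still qualifies, with the residual self-controlled bias shown above. As a check on that residue, also report the self-controlled analysis with inpatient events only.
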